#### **10.b.viv T3 Follow Up For STI Results**

At follow-up approximately 7 days later, we will provide STI results/treatment. Participants will receive \$5 for this visit.

#### **10.d Continuity of Care for those who engage in PrEP**

Following the T3 (last) visit we will offer participants who want to remain in PrEP, standard care using the same clinical staff and facilities for the duration of the study. At study conclusion, we will facilitate transfer of clinical care to an appropriate medical provider. We have developed a list of local PrEP providers who have expressed willingness to work with our population (see Appendix 7). Referral will include provision of the provider list and help with scheduling their first clinical appointment for those expressing this need.

#### **10.e Retention**

To decrease attrition, we will develop a tracking protocol to ensure multiple points of contact with participants. Using their preferred mode of contact, we will remind participants of study visits and follow up with those who "no show." For each "no show," we will follow up twice weekly for 3 weeks. Any participant failing to contact staff within 3 weeks will be considered lost to follow up. However, they will not be withdrawn from the study. Using these procedures, we anticipate >85% retention.

#### **10.f Laboratory Tests**

Philadelphia Department of Health will perform STI testing using the AC2 CT/GC assay on the Hologic Tigris platform, Hepatitis B testing will be performed on the Abbott Architect and creatinine testing will be performed on the Beckman Coulter DXC. Positive test results will be reported to disease control agencies per local regulations. This process is outlined in the informed consent. Philadelphia FIGHT will perform drug-level monitoring using a semi-quantitative liquid chromatography-tandem mass spectrometry urine assay with high sensitivity and specificity to monitor TFV. Specimens will be processed and confidential results returned within 7 days. Pregnancy tests will be performed by the CP using a rapid urine assay to detect human chorionic gonadotropin hormone.

#### **10.e Procedures to lessen the probability or magnitude of risk**

Free treatment for STI: Participants screening positive for STI will receive no cost treatment at their follow-up appointments T1, T2 and T3. Participants screening positive who fail to return for test results and appropriate treatment, will be referred to the Philadelphia Department of Health to arrange treatment. Participants will consent to PDH follow-up if they fail to obtain treatment from the study team during the informed consent process.

Pregnancy: We will provide patients with contraceptive counseling and prescriptions as in the current standard of care for women on PrEP per CDC PrEP clinical guidelines. Women who test positive for pregnancy will be

withdrawn from the study and referred to their primary care provider (PCP). If women do not have a PCP we will work with them to establish care.

**Medication adverse effects:** There is minimal risk of harms associated with the use of daily FTC/TDF as PrEP by HIV-uninfected individuals. Medication intolerance during clinical trials included nausea, vomiting, abdominal pain, and diarrhea. These effects occurred in a minority of PWID (<20%) participating in the Bangkok Tenofovir Trial and most participants reported symptoms had resolved by the 2nd month. Of these side effects, only nausea and vomiting were statistically higher among PWID on Tenofovir than those taking the placebo. Tenofovir has been linked to renal impairment when used for HIV treatment, and a meta-analysis of 3 PrEP efficacy studies found that use of TDF/FTC was associated with small but statistically significant decreases in renal function. However, increased creatinine was observed in only 3% of patients in the Bangkok Tenofovir study, and other studies have found that changes in renal function with use of PrEP are reversible upon discontinuation of TDF/FTC. To monitor for potential medication-related renal toxicity, we will measure creatinine levels at T1 and T2 (which will be scheduled over 3 months) as is recommended in the current CDC PrEP clinical guidelines and is considered standard of care. We will also follow-up with participants accepting a PrEP prescription approximately 2 weeks after T1. During that check-in we will assess for medication intolerances, assess adherence, and provide adherence counseling. Any participant with intolerances (i.e. that do not resolve by 2 months after use of PrEP) or any abnormal renal function testing will be scheduled with the CP. Those with any persistent intolerances or abnormal renal function will be referred to their primary care provider (PCP). If women do not have a PCP we will work with them to establish care.

## 10.f Data Sources

Medical Record/Chart Review       Films/X-rays  
 Computer/Database       Hospital administrative/billing records  
 Quality Improvement Records

*Other types of records please specify:*

**Surveys and interview data. All instruments are included as appendices.**

*Is data ONLY from the clinical department of the PI and sub-I's?*  Yes  No

## 11. DATA AND SPECIMEN BANKING

*Not applicable.*

## 12. DATA MANAGEMENT

### 12a. Data analysis plan

**Aim 1. Describe WWID's engagement in the PrEP care continuum among WWID.** We will use summary statistics (frequency and percent with associated error terms) to describe participant engagement across key transition points in the care continuum including: (1) returning for STI results at T1; (2) enrolling in health insurance or medication assistance programs for uninsured participants between T0 and T2; (3) accepting a PrEP prescription; (4) filling the PrEP prescription or providing authorization for the PrEP prescription to be filled between T0 and T2; (5) adhering to PrEP between T1 and T3; (6) and returning for follow-up care at T2 and T3. Descriptive analyses will also be used to characterize adherence in terms of perfect defined as a dose of TFV within 48 hours (>1000 ng/mL), low adherence (>10 to >100 ng/mL), and non-adherence as defined by last dose more than one week prior (<10 ng/mL). We will also compare concordance of self-reported adherence to urinalysis.

**Aim 2. To assess the impact of predisposing, enabling, and need-related factors on WWID's engagement in the PrEP care continuum.** We will test the association between BMVP factors and WWID's engagement at each stage outlined above using procedures that have been used previously to describe gaps in the PrEP care continuum for MSM. Independent variables will represent each of the model's domains including: predisposing factors, enabling factors, and need (drawn from Table 1). In the case WWID do not populate each stage describe above we will collapse engagement into an ordered categorical variable similar to how we are approaching qualitative data. In this case, engagement would be treated as a 3-level variable: never initiated PrEP vs those who initiate but disengage vs those who remain engaged for 3 months. Inferential statistics will be used to identify associations between factors in the model and PrEP engagement. For

continuous variables, such as age or number of sex partners, we will provide medians with associated interquartile ranges and utilize independent samples t-tests or Mann-Whitney U tests to identify differences in medians between women who do or do not engage at each stage. For categorical and binary variables, such as race/ethnicity or insured (yes/no),  $\chi^2$  tests will be used to detect differences in factors that may be associated with PrEP engagement. Assessing the factors impacting engagement is critical for the design of intervention strategies, as different populations of WWID may need different cues to action or support in order to engage at each stage. These analyses will inform future study designs and sample size.

**Aim 3. To explore how and why model factors are associated with WWID's decisions and ability to engage in PrEP care.** One of the objectives of this study is to determine the relative importance of factors that are facilitators or barriers to PrEP engagement. This will be done using content analysis of qualitative data. To do this, we will explore the relative impact of predisposing, enabling, and need-related factors on PrEP continuum engagement. Interviews will draw on the quantitative findings and provide contextual accounts for how these factors impact decisions about and ability to engage in PrEP care. Data from WWID who never initiated PrEP, those who initiate but disengage, and those who adhere/engage for 3 and for 6 months will be analyzed separately and then compared/contrasted. To create a coding framework for analyzing interview data we will use an iterative process. First, a priori "structured codes" corresponding to the domains in the interview guide will be developed. Second, "emergent codes" that reflect unanticipated factors outside of our conceptual framework will be developed. Two analysts will code each transcript. Discrepancies in coding will be resolved by discussion until inter-rater reliability is >75%. Finally, we will triangulate data with quantitative assessments and member check findings with the CAB to increase the validity of the findings. Analyses will answer the following research questions (this list is not exhaustive): 1) What predisposing, enabling, and need-related factors influence women's decision to initiate (or decline) PrEP and how do they operate? 2) What contextual factors positively (and negatively) impact women's ability to adhere to PrEP? 3) Are there differences in the narratives told within the subpopulations of women (i.e., those with STI, those engaging in transactional sex, or by primary vs secondary exchange clients)? 4) What features of a structural or behavioral intervention could assuage barriers to care and how would they need to operate? 5) What factors are associated with risk compensatory behavior among WWID who initiate PrEP? Our team has experience with similarly structured qualitative data to understand barriers/facilitators and patient preferences for sexual health care and is well equipped to conduct these analysis.

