**1. PROTOCOL TITLE:** Packaging PrEP to Prevent HIV Transmission among Women who Inject Drugs (WWID)

**2. IRB REVIEW HISTORY:** Approved 4/25/17; Modification 7 approved 07/06/2018

**3. OBJECTIVES/AIMS:** This study will address the following objectives or specific aims:

**Aim 1: To describe WWID's engagement in the PrEP care continuum.** Using data from baseline and exit (N=200), we will quantify participant engagement including: (1) attending initial clinical appointment; (2) enrolling in health insurance or medication assistance programs for uninsured participants; (3) accepting a PrEP prescription; (4) filling the PrEP prescription; (5) adhering to PrEP, and (6) returning for follow-up care. These activities represent critical moments when women could disengage or need additional support to remain in care.

**Aim 2: To assess the impact of predisposing, enabling, and need-related factors on WWID's engagement in the PrEP care continuum.** We will test for associations between Behavioral Model for Vulnerable Populations (BMVP) factors and stage of engagement.

**Aim 3: To explore how and why model factors are associated with WWID's decisions and ability to engage in PrEP care.** A subset of WWID representing those who never initiated PrEP (n=15), those who initiate but disengage (n=15), and those who adhere/return for 3 months (n=15) will complete an in-depth qualitative interview that explores individual and structural facilitators and barriers that support or hinder engagement. Interviews will draw on quantitative findings and provide contextual accounts of how factors operate, potential modification of service delivery and targets for behavioral interventions to support engagement.

**Aim 4. To describe sexual behavior and incident STI among WWID.** Using data from baseline, follow-up and exit (N=200), we will describe sexual risk behavior and acquisition of incident infections of syphilis, gonorrhea, chlamydia, and trichomoniasis among WWID. We will test for differences in risk/STI between those who initiated PrEP and those who did not.

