#### **10.b.iv Provision of Prescriptions**

Any insured participant who is interested in PrEP or birth control will be given 2 options for obtaining their prescriptions (should baseline tests indicate they are clinically eligible for PrEP per the CDC guidelines—Creatinine clearance  $\geq 60\text{mL/Min}$ ): 1) the study team will fax prescriptions to Philadelphia Pharmacy who will deliver the PrEP prescription to Prevention Point Philadelphia (Appendices 17, 18) or 2) a paper prescription that the participant will be given so that they may fill it at the pharmacy of their choice. Given the opioid crises in Philadelphia and its impact on study participants, we will also offer a prescription for Naloxone, a medication that rapidly reverses the effects of an opioid overdose which is safe, recommended for use in this population by the CDC, and has been in use in hospitals and ambulances since 1979. Participants will also have the option to receive refills for their prescriptions at PPP. Participants preferring the study team fax the prescription will complete the prescription authorization and release of information form (Appendix 17). Participants who prefer the paper prescription will complete the pharmacy release of information (Appendix 14).

**10.b.v PrEP Check In: For only those who accepted a PrEP prescription** If participants choose to take a prescription for PrEP, we will schedule them for a check in visit to assess tolerance and adherence for approximately two weeks after T1. The “check in” assessment is in Appendix 13. Participants will receive \$5 for this visit.

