#### **10.b.vi Follow-Up Visit (T2)**

T2 will occur approximately 3 months after T1. Participants will self-obtain specimens (throat, urogenital, and rectal) to monitor incident gonorrhea (GC) and chlamydia (CT). Participants will also provide urine and blood specimen to monitor PrEP adherence, creatinine levels, syphilis, pregnancy, and HIV (provided by PPP per their standard of care). PrEP adherence, creatinine levels, and pregnancy testing will only be performed for women taking PrEP. Participants will complete a semi-structured interview to explore psycho-social factors associated with HIV/STI risk, and engagement across key transition points in the PrEP care continuum including (1) attending initial clinical appointment; (2) enrolling in health insurance or medication assistance programs for uninsured participants; (3) accepting a PrEP prescription; (4) filling the PrEP prescription; (5) adhering to PrEP using a validated three-item self-report measure for anti-retroviral therapy adherence in the last 30 days, modified for PrEP adherence, (6) and returning for follow-up care. These activities represent critical moments when women could disengage or need additional support to remain in care. If participants disengage in care at any point in the PrEP continuum, we will ask about the factors motivating this decision. Then, we will assess the acceptability of receiving PrEP care at the SEP, intention to remain engaged in PrEP care, and the factors motivating them to do so (or drop out of care). A draft of the semi-structured interview is in Appendix 3. Participants will receive \$25 for this visit. Any participant needing clinical follow-up after T2 will be scheduled with the CP outside of study hours. Women who test positive for pregnancy will not be eligible for follow-up PrEP care at PPP. They will be referred to their primary care provider (PCP). If women do not have a PCP we will work with them to establish care.

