#### **10.b.viii Follow-Up Visit (T3)**

T3 will occur approximately 3 months after T2. Participants will self-obtain specimens (throat, urogenital, and rectal) to monitor incident gonorrhea (GC) and chlamydia (CT). Participants will also provide blood specimen to

monitor creatinine levels (if someone is taking PrEP only), syphilis and HIV (provided by PPP per their standard of care). Urine specimen will be collected to monitor pregnancy for women taking PrEP. They will also sign a release of information (Appendix 14) to allow us to contact the pharmacy where they report filling their PrEP prescription to verify fill dates. Participants will complete a semi-structured interview to explore psycho-social factors associated with HIV/STI risk and engagement across key transition points in the PrEP care continuum. If participants disengage in care at any point in the PrEP continuum, we will ask about the factors motivating this decision. Then, we will assess the acceptability of receiving PrEP care at the SEP, intention to remain engaged in PrEP care, and the factors motivating them to do so (or drop out of care). A draft of the semi-structured interview is in Appendix 15. Participants will receive \$35 for this visit. Any participant needing clinical follow-up after T3 will be scheduled with the CP outside of study hours. Women who test positive for pregnancy will not be eligible for follow-up PrEP care at PPP. They will be referred to their primary care provider (PCP). If women do not have a PCP we will work with them to establish care.

We will also recruit a purposive sample of WWID who initiate but disengage (n=15) and WWID who adhere/remain engaged in PrEP for 6 months (n=15) to participate in an in-depth qualitative interview. Recruitment will be done so that we elicit diversity in opinions, challenges, and successful strategies to engagement. Interviews will elicit previously unmeasured but critical factors impacting women's decisions and will also explore individual and structural facilitators and barriers that hinder or support engagement at each stage of the care continuum drawing from the BMVP. A preliminary draft of the in-depth interview is in Appendix 5. This subset of participants will receive \$20 for participating in the qualitative interview.

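### The analysis plan lets an authorization count as filling the PrEP prescription (stage 4), so the stage probably measures different events on the fax and paper routes

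*Combined protocol and SAP*

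**What the plan says.** Section 3 (Aim 1) lists the fourth continuum step as "4) filling the PrEP prescription". Section 10.b.vi, on the T2 interview, has the same item: "4) filling the PrEP prescription; (5) adhering to PrEP using a validated three-item self-report measure". Section 12a, which sets the measures and time windows for Aim 1, widens it to "4) filling the PrEP prescription or providing authorization for the PrEP prescription to be filled between T0 and T2". Accepting a prescription is already counted separately, as stage 3.

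Section 10.b.iv gives two routes. On the first, "the study team will fax prescriptions to Philadelphia Pharmacy who will deliver the PrEP prescription to Prevention Point Philadelphia". On the second, the woman takes a paper prescription to a pharmacy of her choice. The paperwork differs by route: "Participants preferring the study team fax the prescription will complete the prescription authorization and release of information form (Appendix 17"), whereas "Participants who prefer the paper prescription will complete the pharmacy release of information (Appendix 14").

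Information on actual fills is planned. The T2 interview covers filling, and at T3 (section 10.b.viii) "They will also sign a release of information (Appendix 14) to allow us to contact the pharmacy where they report filling their PrEP prescription" and verify the dates. Section 12a does not tie either source to stage 4. Its Aim 2 text then tests factors against each of the stages listed for Aim 1.

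**The concern.** The continuum is meant to show where women leave care, and section 9 says the findings will shape an intervention for each stage. If signing a form satisfies the filling stage for some women, stage 4 nearly repeats stage 3 for them. A prescription that was faxed but never dispensed is then recorded as filled, and the loss first appears at stage 5. That suggests an adherence barrier where the real barrier is access to the drug.

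The combined percentage would also move with the share of women choosing the fax route, even if filling were equally common on both routes. Aim 2 inherits the problem: a factor related to choice of route could look associated with filling.

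**Working it through.** **1. The text.** Sections 3 and 10.b.vi name filling alone; section 12a names filling or authorization. All three are current text. Section 12a does not mention routes. The link to the fax route is an inference from section 10.b.iv, where only the faxed prescription has a form described as an authorization and the paper prescription has only a pharmacy release.

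**2. Inputs.** The plan states no figure for stage 4, so there is none to reproduce. Three quantities are needed and none is in the documents, so all are assumptions: s, the share of acceptors on the fax route; f, the share of faxed prescriptions dispensed; p, the share of paper prescriptions filled.

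**3. Excess with complete ascertainment.**

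- Rate as section 12a scores it: s + (1−s)p
- Rate of actual fills: sf + (1−s)p
- Difference: s(1−f), whatever p is

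| Excess, percentage points | f = 1 | f = 0.9 | f = 0.7 |
|---|---|---|---|
| s = 0.3 | 0 | 3 | 9 |
| s = 0.5 | 0 | 5 | 15 |
| s = 0.7 | 0 | 7 | 21 |

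For scale, section 12b's planning figures give 200 × 0.86 × 0.50 = 86 initiators. If 86 is also taken as the number of acceptors, 5 and 15 points are about 4 and 13 women (86 × 0.05 = 4.3; 86 × 0.15 = 12.9). The 95% half-width for a rate of 70% is 1.96 × √(0.7 × 0.3 / 86) = 9.7 points; for 90% it is 6.3 points. The excess at s = 0.5 is thus below sampling error at f = 0.9 and above it at f = 0.7.

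**4. Aim 2.** With equal fill rates on both routes (p = f), the scored rate is f + s(1−f). Take two levels of a factor that has no effect on filling but whose fax shares differ by 10 points. Their stage-4 rates differ by 10(1−f): 0, 1 or 3 points at f = 1, 0.9 or 0.7.

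**5. Would a fill-only count be enough?** Suppose only a share c of fills can be confirmed and the rest are scored as not filled. With c = 0.85 (illustrative; section 12b assumes 15% attrition per visit), s = 0.5, p = f and equal capture on both routes:

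- Current wording: error = s(1−f) − (1−s)f(1−c)
- Fill-only: error = −f(1−c)

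| Error, percentage points | f = 1 | f = 0.9 | f = 0.7 | f = 0.5 |
|---|---|---|---|---|
| Current wording | −7.5 | −1.75 | +9.75 | +21.25 |
| Fill-only, unconfirmed = not filled | −15 | −13.5 | −10.5 | −7.5 |

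Under these assumptions the current wording has the smaller error in three of the four cases. Deleting the authorization clause and scoring the unconfirmed as failures is therefore not a safe repair.

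**6. Bounds.** If 15% of acceptors have unknown fill status, the two extreme counts are 0.85f and 0.85f + 0.15. At f = 0.7 they are 59.5% and 74.5%; at f = 0.9, 76.5% and 91.5%. Each interval contains the true rate, and its width shows how much is unknown.

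**The case against.** The best defence is that the clause is deliberate. Section 12a is the place for operational definitions, and sections 3 and 10.b.vi only list activities and interview topics. The aim is to describe participants' engagement. On the fax route, authorizing is the woman's own act; the study team and the pharmacy do the rest. That is a reasonable purpose, and it supports reporting authorization. It does not support merging it with filling, and no section explains the change.

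It is also fair that the study is exploratory, that the Aim 2 effect is small per 10 points of fax share, and that stage 4 would cease to be a separate outcome if engagement is collapsed to three levels. Fill data are already planned, so the matter can be corrected at reporting. These points limit the seriousness but leave the mismatch in place.

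Three stronger readings are tempting and not supported:

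- **That the excess is large.** Reaching 25 points at s = 0.5 needs f = 0.5, that is, half of faxed prescriptions never dispensed. Nothing in the documents suggests this. Section 12b expects about half of willing women to initiate but does not say at which step the others stop, and the fax route spares women a trip to the pharmacy.
- **That the stage-4 figure is an upper bound on filling.** Missed paper-route fills would push it down. That is a separate ascertainment question, and it is eased by the check-in about two weeks after T1 (section 10.b.v) and by the release signed with the paper prescription.
- **That a fill-only count must be more accurate.** Step 5 of the working shows otherwise when unconfirmed fills are scored as failures.

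**Conclusion.** The inconsistency is real: stage 4 is filling in two sections and filling or authorization in the analysis plan. Followed as written, a woman can meet the filling stage with nothing dispensed. That this divides along the fax and paper routes is probable but not established, since Appendices 14 and 17 are not available here.

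The size is unknown. With complete ascertainment it is s(1−f): zero if every faxed prescription is dispensed, and 5 or 15 points at s = 0.5 with f = 0.9 or 0.7. These are illustrations, not estimates. The change should be made because the rule can place drop-off at the wrong stage of the study's main descriptive outcome and carry route choice into Aim 2, and because it costs little. It does not undermine the rest of the plan.

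**What to change.** - Reconcile sections 3, 10.b.vi and 12a on stage 4, and define it as a confirmed fill on both routes.
- State the order of sources: pharmacy fill dates (section 10.b.viii) first; otherwise the T2 interview (section 10.b.vi); with the two-week check-in (sections 10.b.v and 10.e, medication adverse effects) as supporting information.
- Where their scope allows, use the releases signed under section 10.b.iv, so that checking a fill need not wait for T3. On the fax route the pharmacy is already known.
- Report *authorized, fill not confirmed* as a separate line, and show stage 4 by route.
- Do not simply score unconfirmed fills as not filled. Give the rate with them counted as all filled and as none filled.
- Run the Aim 2 stage-4 tests on the fill outcome, with the same two bounds as a sensitivity check.

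The cost is a revised definition, one more table line and a split by route, from data largely planned already. The stage-4 rate may be lower, and some fills among women lost to follow-up will stay unverifiable. If the T2 interview were the only source, 15% attrition per visit would leave 15% of acceptors without it when acceptance is counted from T1, and 1 − 0.85² = 28% when counted from T0. Section 10.e (Retention) is more hopeful ("we anticipate >85% retention"); if that is an overall figure, fewer than 15% would be lost. Pharmacy checks under the releases signed with the prescription would reduce the gap, if Appendices 14 and 17 permit them.

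### Aim 1 counts insurance cover and filling only to T2 but follows adherence and return to T3, so a first cover or first fill in months 4 to 6 is recorded as non-engagement

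*Combined protocol and SAP*

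**What the plan says.** Section 12a, Aim 1, lists six stages of the care continuum. Their time limits differ.

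- Stage 2 is "enrolling in health insurance or medication assistance programs for uninsured participants between T0 and T2".
- Stages 3 and 4 run on as "3) accepting a PrEP prescription; (4) filling the PrEP prescription". No window is attached to stage 3.
- Stage 4 in full is "filling the PrEP prescription or providing authorization for the PrEP prescription to be filled between T0 and T2", so either a fill or an authorization satisfies it.
- Stage 5 is "5) adhering to PrEP between T1 and T3".
- Stage 6 is "returning for follow-up care at T2 and T3".

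On visit timing, Section 10.b.vi says "T2 will occur approximately 3 months after T1" and Section 10.b.viii says "T3 will occur approximately 3 months after T2". Section 10 calls T3 the exit visit and puts it about six months after T1. Section 3 introduces Aim 1 with "Using data from baseline and exit (N=200". Under Aim 2, Section 12a makes engagement at each of these stages an outcome to be tested against the model factors. Insured (yes/no) is one of the example variables.

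The plan gives no reason for the T2 cut-off. It does not state a denominator for any stage, and it does not say whether a stage is conditional on the one before.

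**The concern.** A care continuum is read as the loss from one step to the next. That reading needs the steps to be observed over the same period, or the difference in periods to be stated and justified. Here the middle steps close about three months after T1 and the last two stay open for about three months more.

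Late entry is plausible on the documents' own description. Section 10.b.iv describes the ways of obtaining a prescription for insured participants and sets no closing date. A woman whose cover is slow to arrive is therefore a natural late starter.

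Two results are at stake. In Aim 1, a late cover or late fill appears as a permanent loss at that step. In Aim 2, the same woman is placed with those who did not engage, so a factor that slows access looks like a factor that blocks it. Section 9 says the findings will shape a tailored intervention to raise engagement at each stage, and delay and refusal call for different responses.

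**Working it through.** The documents give no figure for this point, so there is none to reproduce. The check sets the windows beside the visit times and then follows individual women through them.

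**Step 1: windows on one time scale.** T2 is about 3 months after T1. T3 is about 3 + 3 = 6 months after T1, which agrees with Section 10.

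| Stage (Section 12a, Aim 1) | Window | Months 4 to 6 counted? |
|---|---|---|
| 2. Cover | T0 to T2 | No |
| 3. Accepting a prescription | none stated | Not excluded |
| 4. Fill or authorization | T0 to T2 | No |
| 5. Adherence | T1 to T3 | Yes |
| 6. Return | T2 and T3 | Yes |

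The uncounted period for stages 2 and 4 is 6 − 3 = 3 months, half of the follow-up after T1.

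**Step 2: women followed through the rules as written.** I read the T0 to T2 limit as applying to both halves of stage 4.

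- *Uninsured at T0, first covered in month 4, fills in month 4.* She fails stage 2. She also fails stage 4 unless she had authorized a fill by T2, which is unlikely because Section 10.b.iv describes the fax authorization for insured women.
- *Accepts at T0, neither fills nor authorizes by T2, fills in month 5.* She passes stage 3 and fails stage 4.
- *First accepts in month 4 and fills the same day.* She passes stage 3, which has no limit, and must fail stage 4. The drop between the two stages is produced by the windows.
- *Authorizes by T2, first fills in month 4.* She passes stage 4 and is not affected.

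**Step 3: are the later data collected?** Largely yes. Section 10.b.viii has a T3 interview covering the transition points of the continuum, and a release under which pharmacies confirm fill dates. Section 10.a gives access to the syringe exchange program's case-management records on insurance enrolment.

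**Step 4: can the number affected be derived?** No. The power section (12b) gives 86% willing and 50% of those initiating, so 200 × 0.86 × 0.50 = 86 initiators. No time limit is attached to the 50%. The 86 may be starts by T2 only, or may already include later ones, and nothing in the documents separates them. What can be said is the effect per woman: if the denominator is all 200, each woman affected moves the stage 4 percentage by 1/200 = 0.5 points.

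**The case against.** The best defence is that uptake within about three months, followed by persistence to six, is a coherent definition, and that late first fills should be uncommon. PrEP is offered at baseline (Section 10). Eligibility for a prescription rests on baseline tests, and the check-in falls about two weeks after T1 (Sections 10.b.iv and 10.b.v). The T2 and T3 procedures describe no renewed offer to women not taking PrEP. A percentage labelled T0 to T2 is also correct for what it claims, and Section 12b calls the study exploratory. All of this limits the size of the problem. It does not explain why stage 3 is open-ended, or why Aim 1 is said to use exit data while two of its stages stop at T2.

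A reader might infer more than the documents support, in three ways.

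- *That a late filler would be coded a non-filler yet counted as adherent and retained.* Section 10.b.viii lists T3 urine only for pregnancy, so the drug-level categories in 12a would not be available for her. The three-item self-report measure is described only at T2. The plan does not say whether stage 5 depends on stage 4. Stage 6 can be met by any participant, because T2 and T3 are scheduled whether or not she started PrEP. That is a matter of unstated denominators, and moving the cut-off would not cure it.
- *That she is an initiator for Aim 4.* Section 3 does not define initiation or give it a window.
- *That a range of misclassified women can be given.* Any such range rests on an assumed late-fill rate and on a choice about what the 86 already contains.

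**Conclusion.** The point holds as an inconsistency between stated windows. Followed as written, the plan records as not engaging any woman first covered after T2 (stage 2), and any woman who neither filled nor authorized by T2 and first does so between T2 and T3 (stage 4). This carries into both Aim 1 and Aim 2.

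The number is unknown and may be small; I give no range. The conclusion assumes that women can still obtain cover or a first prescription after T2. The documents do not rule this out, but they do not describe a route for it either.

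The windows may be left over from a three-month design. Section 10 still opens with three months of follow-up, and the three-level fallback in Aim 2 is defined at three months, whereas Aim 3 in Section 12a refers to both three and six. That is an inference, and a deliberate T2 definition remains possible. Nothing in the study is invalidated, but the windows should be reconciled before the continuum is tabulated.

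**What to change.** In Section 12a:

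- Report stages 2, 3 and 4 both by T2 and by T3, using the T3 interview, the pharmacy fill dates verified at T3 and the case-management records.
- Show the six-month continuum with the T3 window for all stages. If a three-month continuum is also wanted, cut every stage at T2. Stage 1 is a T1 event and is unchanged.
- State the denominator for each stage and whether it is conditional on the stage before.
- Use the same windows for the stage outcomes in Aim 2.

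The cost is a wording change and one extra tabulation, mostly from data already planned. The downside is less complete status after T2. Section 12b expects 15% attrition at each visit. The insurance release in Section 10.b.ii covers whether a woman was signed up and does not mention the date, so enrolment dates may not be recorded. The number with missing T3 status should be shown beside each T3 percentage.
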